The complete response and complete/partial response rates will be reported by study arm and chemotherapy regimen using Wilson 95% confidence intervals. The responses rates will be compared between study arms using the CMH exact test.

The tCLN (tethered cationic lipoplex nanoparticle biochip), mCLN (microfluidic cationic lipoplex nanoparticle biochip) and qRT-PCR (real-time quantitative reverse transcription-polymerase chain reaction) measurements for the expression of miR-1, -21, -127 and -155 will be made on sera collected from NSCLC patients with and with no radiation pneumonitis. The miR expressions, vitamin D levels, and mitochondrial DNA levels will be treated as continuous and reported by radiation pneumonitis status (no versus yes) using the mean, median and standard deviation. Comparisons will be made between groups using a two-sided permutation t-test, as there is no a priori notion of which group will have higher expression.

A pilot model, using the 4 miR expression levels as the biomarker, will be built for classification of patients into 1 of 2 patient populations: radiation pneumonitis versus no radiation pneumonitis. Two classification models will be considered. The first model will treat the miR expressions as dichotomous variables, where the Youden's index method will be used to identify an appropriate threshold. The resulting threshold will maximize the correct classification rate a given miR expression alone was used to classify patients. The second model will treat the miR expressions as continuous variables. Both classification models will be constructed in a similar

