fashion using multivariate logistic regression, such that the resulting model predicts the probability of radiation pneumonitis. A set of candidate variables will be obtained from miR expressions and relevant patient characteristics (demographic and clinical). Standard variable reduction techniques will be applied if the number of candidate variables grows large. The variables in the final model will be selected from the set of candidate variables, including possible two-way interaction terms, using forward selection (alpha entry = 0.05) followed by backward elimination (alpha exit = 0.05). Models are fit using Firth's penalized function and model assumptions are verified graphically. Standard bootstrap and cross-validation techniques will be used to calibrate model coefficients. Model performance will be evaluated using calibration plots, receiver operating characteristic (ROC) curves, area under the ROC curve (AUC) and a decision curve. In both models the Youden's index method can also be used to determine the optimal threshold probability for classifying patients, from which standard classification measures can be obtained (sensitivity, specificity, positive predictive value and negative predictive values). As an alternative modeling strategy, classification and regression tree (CART) analysis may also be considered to develop a model using only the miR expressions. These analyses will be repeated using vitamin D, cytokine and mitochondrial DNA levels, alone and in combination with miR expression, to develop classification models.

All secondary analyses will be conducted in SAS v9.4 (Cary, NC), except for CART analysis conducted in R v2.12, at a significance level of 0.05.

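### Youden cut-offs found and tested on the same patients let a useless miRNA into the model about 3 to 4 times in 10, and the plan misstates what such a cut-off maximises

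*Combined protocol and SAP*

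**What the plan says.** Section 13.7 describes "A pilot model, using the 4 miR expression levels as the biomarker", meant to classify patients as having or not having radiation pneumonitis. Two versions are planned. For the dichotomous version, "The first model will treat the miR expressions as dichotomous variables", and Youden's "index method will be used to identify an appropriate threshold". The plan then claims for this threshold: "The resulting threshold will maximize the correct classification rate a given miR expression alone was used to classify patients".

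Both versions are built by logistic regression with Firth's penalty. Variables are chosen "using forward selection (alpha entry = 0.05) followed by backward elimination (alpha exit = 0.05". For internal validation the plan says: "Standard bootstrap and cross-validation techniques will be used to calibrate model coefficients". Performance is to be reported as AUC, sensitivity, specificity and predictive values. The same steps are to be repeated for vitamin D, cytokines and mitochondrial DNA, alone and together with the miRNAs.

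No hold-out sample, external cut-off or adjusted p-value for an optimised cut-off is mentioned. The direction of effect is left open too: the two-group comparisons are two-sided "as there is no a priori notion of which group will have higher expression".

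**The concern.** There are two separate errors.

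The first is the property claimed for the cut-off. Youden's index is sensitivity + specificity − 1. It gives equal weight to the two outcome groups whatever their sizes, whereas the correct classification rate weights them by how common they are. At the event rates this trial expects, the two criteria point to very different thresholds.

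The second is the p-value. The cut-off is searched for the best separation of patients with and without pneumonitis. The resulting binary marker is then tested at 0.05 as though the cut-off had been fixed beforehand. Choosing the best of many splits and then testing that split gives far more false entries than 5%. Resampling is stated for the coefficients; nothing says that the cut-off search or the variable selection is redone in each resample, so nothing written removes the optimism from the reported AUC, sensitivity and specificity.

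Finding markers of pneumonitis risk is the exploratory objective (Section 3.3). A procedure that usually yields a nominally significant miRNA with a cut-off when none matters cannot serve it, and a later study could adopt that cut-off.

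**Working it through.** **Inputs.** At most 99 randomised patients, 33 placebo and 66 nintedanib (Sections 13.1 and 13.7). Pneumonitis rates of 30% and 10% (Section 13.1). Four miRNAs, entry and exit alpha 0.05, Firth fitting, no prior direction (Section 13.7). The plan gives no operating characteristics for the biomarker models, so the only stated figure to compare with is the nominal 0.05.

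**Expected events.** Under the planned effect: 0.30 × 33 + 0.10 × 66 = 9.9 + 6.6 = 16.5, about 17. With no treatment effect: 0.30 × 99 = 29.7, about 30.

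**Part 1: what the cut-off maximises.** With event prevalence π, accuracy = π × sensitivity + (1 − π) × specificity. At π = 0.5 this is (J + 1)/2, where J is Youden's index, so the two criteria agree. At other prevalences they need not.

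Take a genuinely useful marker, normal in both groups with AUC 0.70. The groups are separated by √2 × Φ⁻¹(0.70) ≈ 0.74 SD. The Youden cut lies midway, at 0.37, where sensitivity = specificity = Φ(0.37) ≈ 0.645.

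| Prevalence | Accuracy at Youden cut | Maximum accuracy |
|---|---|---|
| 16.7% | 64.5% | 83.5% |
| 30% | 64.5% | 72.0% |
| 50% | 64.5% | 64.5% |

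These are population values. In simulated samples of 99 with 17 events, the apparent accuracy at the fitted Youden cut averaged 68%. Calling every patient negative is correct for 82/99 = 83%, and the Youden cut fell below that in 91% of runs.

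**Part 2: false entry of a useless marker.** Noise markers (20,000 per setting, n = 99) were cut at the largest Youden index with direction taken from the data, then tested at 0.05. The plan does not name the entry test, so three were used. For a 2×2 table the Firth penalised likelihood-ratio test equals the likelihood-ratio test after adding 0.5 to each cell.

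| Test at 0.05 | 17 events | 30 events |
|---|---|---|
| Score | 38% | 38% |
| Firth penalised LR | 36% | 37% |
| Firth Wald | 27% | 31% |
| Score, marker kept continuous | 5.0% | 5.0% |

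Fisher's exact test gave 28% at 17 events. Entry by score followed by retention by Wald gave 27%, so backward elimination does not rescue the procedure. The mean apparent Youden index was 0.22 when the truth is 0. A median split fixed in advance gave about 3% to 5%.

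**Any of four independent useless markers.** The chance is 1 − (1 − p)⁴:

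- score, 17 events: 1 − (1 − 0.381)⁴ = 0.85
- penalised LR, 17 events: 1 − (1 − 0.356)⁴ = 0.83
- Wald, 17 events: 1 − (1 − 0.276)⁴ = 0.73
- score, 30 events: 1 − (1 − 0.386)⁴ = 0.86
- at a true 0.05 each: 1 − 0.95⁴ = 0.185

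**Sensitivity of the single-marker rate.**

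- 12 to 40 events in 99: 34% to 40% (score or penalised LR), 26% to 32% (Wald).
- Cut restricted to the central 60% of values: 21% to 31%.
- Direction fixed in advance: 15% to 22%.
- Trial stopped at 33 patients: 28% to 34% (score or penalised LR), 12% to 14% (Wald).

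**The case against.** The strongest reply is that this is a pilot model under the only exploratory objective, with no trial decision resting on it. That limits the severity but does not make the procedure sound, because the output of a pilot is the marker and cut-off that it passes on.

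The plan also compares the miRNAs, vitamin D and mitochondrial DNA as continuous variables with a permutation t-test, and fits a second model with the miRNAs continuous. Neither suffers from the cut-off search, and a false hit in the dichotomous model might sit beside two null results. That is a real safeguard for a careful reader. It does not repair the dichotomous model, and the plan gives neither model priority.

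The sentence on resampling neither states nor excludes repeating the cut-off search and selection. That is fair: use of the same data is inferred, because no other source is named. If nested resampling was intended, one sentence would settle it.

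The any-of-four figure assumes independent markers. At an assumed correlation of 0.8 it falls to 63% to 74%. Part of it is ordinary multiplicity, which alone gives 18.5%. Both points stand, and the per-marker rate does not depend on them.

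The classification sentence lacks a word and might loosely mean the average of the two group-specific correct rates, which Youden's index does maximise. Read as written, it is wrong. Calling everyone negative has zero sensitivity, so the accuracy comparison shows that the stated property is false, not that Youden's index is a poor criterion.

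**Conclusion.** The concern holds on both parts. At the planned size and event rates, the dichotomous model admits a useless marker in about 27% to 38% of data sets instead of 5%, and at least one of four independent useless markers in about 73% to 86%. The claim that the threshold maximises correct classification is false at event rates of 10% to 30%.

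The figures assume that all 99 patients contribute samples, that the cut-off and the test use the same patients, that direction is taken from the data, and that markers are tested singly, without the clinical covariates and interactions that the plan also allows. The range reflects the unnamed entry test. The damage is confined to the exploratory biomarker work. This should be corrected before analysis, but it does not threaten the primary comparison.

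**What to change.** In Section 13.7:

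- Name the continuous-marker model as the main miRNA model and apply the 0.05 entry level there.
- If the dichotomous model is kept, repeat the cut-off search and the variable selection inside every bootstrap or cross-validation sample. Report only optimism-corrected AUC, sensitivity and specificity, and attach no nominal p-value to a cut-off derived from the data.
- Replace the sentence on correct classification with a statement that the threshold maximises the sum of sensitivity and specificity.
- Apply the same rules to vitamin D, cytokines and mitochondrial DNA.

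The cost is SAP wording and some computing, with no extra patients, samples or visits. Reported marker performance will look less favourable.

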13.1 Sample Size Determination

A maximum of 18 participants will be enrolled to the non-randomized dose escalation portion of this study. The number of participants required is a function of the unknown dose-toxicity relationship.

A maximum of 99 participants will be enrolled to the randomized Phase 2 portion of this study (excluding patients replaced due to ineligibility or inability to start therapy). Participants will be randomized in a 1:2 fashion, stratified by chemotherapy regimen (i.e., platinum with etoposide, platinum with taxane, platinum with pemetrexed) and immune therapy (i.e. durvalumab), into the placebo and nintedanib arms. Accrual is expected to take 4 years.

Evaluable patients will be any patient who receives at least one dose of study drug.

The sample size justification is based on the primary analysis: a comparison of the rate of radiation pneumonitis at 6 months after completion of chemoradiation between the placebo and nintedanib arms, stratified by chemotherapy regimen (i.e., platinum with etoposide, platinum with taxane, platinum with pemetrexed) and immune therapy exposure (i.e. durvalumab), using the one-sided Cochran-Mantel-Haenszel (CMH) exact test at a significance level of 0.05. The expected rate of Grade 2 or higher radiation pneumonitis is 30% in the placebo arm, and a decrease in this rate to 10% in the nintedanib arm would be considered clinically significant; which is equivalent to a common odds ratio (COR) of approximately 0.26.

Using a simulation based on the proposed study design; if there is no improvement in the rate of radiation pneumonitis (COR = 1.0), then there is a 59.0% chance of stopping early for futility. If the true COR is 0.26, then there is only a 10.6% chance of stopping early for futility. If the true common odds ratio is 0.26, then there is an 80.1% chance of detecting a significant reduction in the rate of Grade 2 or higher radiation pneumonitis in the nintedanib arm. If the COR is 1.0, then the chance of detecting a significant reduction is 4.2%; which can be considered the effective type-I error rate.

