13.7 Secondary Analyses

The OS and PFS will be reported by study arm using standard Kaplan-Meier methods. Comparisons of OS and PFS between study arms may utilize the two-sided stratified log-rank test. With a sample size of $n = 33$ in the control and $n = 66$ in the treatment group, there is an 80% chance of detecting a hazard ratio of 0.53 or smaller (with two-sided alpha of 0.05). If the

median PFS in the placebo arm is approximately 2 months, then this would be equivalent to detecting an increase in PFS of at least 1.75 months.

The overall and sub-category QOL and symptom scores (ranging from 0 to 68) will be reported by study arm and time using the appropriate descriptive statistics. Changes in the QOL and symptom scores may be compared between study arms using the Wilcoxon rank sum or independent sample t-tests, as appropriate. No adjustments for multiple testing will be made as this is a secondary analysis. With this sample size, there will be an 80% chance of detecting a change of at least 0.5 standard deviations. A 0.5 standard deviations is equivalent to approximately 9.1 points for the overall QOL and symptoms score; therefore, this study should be able to identify clinically relevant changes in QOL (59).

The PFTs will be reported by study arm and time using the appropriate descriptive statistics. Changes in PFTs, relative to baseline, will be evaluated within each study arm using the Wilcoxon signed rank or paired t-tests, as appropriate. Changes in PFTs may be compared between study arms using the Wilcoxon rank sum or independent sample t-tests, as appropriate. No adjustments for multiple testing will be made as this is a secondary analysis. With this sample sizes, we will have an 80% chance of detecting a change of at least 0.5 standard deviations.

The RP scores will be reported by study arm and time using the appropriate descriptive statistics. Changes in RP scores, relative to baseline, will be evaluated within each study arm using the Wilcoxon signed rank or paired t-tests, as appropriate. Changes in RP scores may be compared between study arms using the Wilcoxon rank sum or independent sample t-tests, as appropriate. No adjustments for multiple testing will be made as this is a secondary analysis. With our sample sizes, we will have an 80% chance of detecting a change of at least 0.5 standard deviations.

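### Section 13.7 selects the biomarker models by stepwise search on about 17 events but does not require selection to be repeated in the resampling, so the reported AUC and classification measures would be optimistic

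*Combined protocol and SAP*

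**What the plan says.** Section 13.7 describes "A pilot model, using the 4 miR expression levels as the biomarker", in two versions: one with each miR dichotomised at a Youden cut-point, one with the miRs continuous. The candidates are the miRs plus relevant demographic and clinical characteristics, which are neither listed nor counted. The selection rule is "The variables in the final model will be selected from the set of candidate variables, including possible two-way interaction terms, using forward selection" with entry at 0.05, followed by backward elimination at 0.05. No rule says whether an interaction may enter without its main effects. Fitting uses Firth's penalty. Variable reduction is promised if the candidates become numerous, with no trigger or method.

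On resampling there is one sentence: "Standard bootstrap and cross-validation techniques will be used to calibrate model coefficients". Performance is then to be judged by calibration plots, ROC curves, AUC and a decision curve, with Youden thresholds giving sensitivity, specificity and predictive values. The section does not say that these are corrected for optimism, or that selection and cut-points are redone in each resample. It names no separate validation sample. The exercise is then extended: "These analyses will be repeated using vitamin D, cytokine and mitochondrial DNA levels, alone and in combination with miR expression".

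Section 3.3 makes the biomarker objective exploratory.

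**The concern.** A model whose terms were chosen because they fitted the data looks better on those data than on new patients. The gap grows with the number of terms searched and shrinks with the number of events. Here events are few and the search may be wide.

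Firth's penalty deals with sparse data and separation; it does not undo selection. Calibrating coefficients does not cure the AUC either: shrinking all slopes by one positive factor leaves the ranking of patients, and so the AUC, unchanged.

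At stake is which markers are carried forward. Section 1.5 hopes to predict pneumonitis risk and to identify patients who may benefit from nintedanib. An uncorrected AUC near 0.7 could come from a useful marker or from noise, and the thresholds and predictive values attached to it might not repeat. The primary comparison is untouched.

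**Working it through.** **Stated figure.** The plan gives no event count, false-selection rate or AUC for these models, so there is nothing to reproduce.

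**Events.** Section 13.1 gives 30% (placebo) and 10% (nintedanib); section 13.7 gives arms of 33 and 66.
- Design rates: 0.30 × 33 + 0.10 × 66 = 9.9 + 6.6 = 16.5, about 17.
- No drug effect, full accrual: 0.30 × 99 = 29.7, about 30.
- No drug effect, stopped at the 33-patient interim (which section 13.1 puts at 59.0%): 0.30 × 33 = 9.9, about 10. This case was not simulated.

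**Terms searched.** With k candidates and all two-way interactions, the number of terms is k + k(k − 1)/2: 10 for k = 4, 36 for k = 8, 55 for k = 10, 136 for k = 16. As a rough guide, if each term had an independent 5% chance of entry, at least one would enter with probability 1 − 0.95^10 = 0.40 or 1 − 0.95^36 = 0.84.

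**Assumed numbers of characteristics.** The plan gives none. I took 0, 4 and 6. The 16-candidate case is four miRs, vitamin D, mitochondrial DNA, the four cytokines named in section 1.5 and six characteristics.

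**Null simulation.** 99 patients, 17 events, no candidate related to outcome, Firth logistic fits, score-test entry and Wald removal at 0.05, no prior variable reduction. The main grid used 400 datasets per setting (150 for 16 candidates). Ranges span separate sets of runs. The Monte Carlo standard error of a 78% rate on 400 datasets is √(0.78 × 0.22/400) = 0.02.

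Continuous miRs: chance that a model is selected, with median apparent AUC when one is.

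| Candidates | Interactions enter freely | Main effects required first |
|---|---|---|
| 4 miRs | 31% (0.68–0.69) | 17% |
| 4 + 4 characteristics | 71–78% (0.73–0.74) | 26% |
| 4 + 6 characteristics | 86–89% (0.76–0.78) | 32% |
| 16 | 99% (0.93) | 46% |

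In the right-hand column the median apparent AUC is 0.68–0.69 throughout. The chance of both a model and an AUC of about 0.70 or more is 13% with the miRs alone, 55–71% with four to six characteristics and free interactions, and 7–15% with main effects required first.

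MiRs dichotomised at Youden cut-points, with 0, 4 and 6 characteristics:
- Free interactions: 80%, 95% and 97% (median AUC 0.70, 0.78, 0.82).
- Main effects required first: 71%, 78% and 79% (0.69–0.70).

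**At 30 events.** Continuous miRs with free interactions give 29% (0.65), 75% (0.70), 90% (0.75) and 99% (0.91) down the four rows.

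**Does resampling rescue it?** In a further 600–800 null datasets with free interactions and 10-fold cross-validation, the median AUCs among datasets that selected a model were:

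| Candidates | Apparent | Coefficients only resampled, after selection | Selection repeated in each fold |
|---|---|---|---|
| 4 + 4 | 0.73 | 0.70 | 0.51 |
| 4 + 6 | 0.77 | 0.74 | 0.49 |

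Resampling the coefficients alone keeps (0.70 − 0.50)/(0.73 − 0.50) = 87% of the excess in the first row and (0.74 − 0.50)/(0.77 − 0.50) = 89% in the second.

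**The case against.** The strongest reply is that the high selection rates are not properties of the plan. They need several characteristics in the pool and interactions free to enter without main effects, and section 13.7 specifies neither. With the miRs alone, or with main effects required, a continuous noise model appears in a minority of runs. The plan also promises variable reduction, which the simulations left out. This stands: a reader might infer that the plan will nearly always find a model in noise, and the documents do not support that. The reduction step, however, has no stated trigger or method, and if it looks at the outcome it is one more step to be validated.

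Second, the text does not say that performance will be read in-sample. A reader might infer that the plan rules out corrected performance. It does not; it never requires it, and names resampling for another purpose.

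Third, the model is a pilot under an exploratory objective, and section 13.7 separately compares miRs, vitamin D and mitochondrial DNA by pneumonitis status with permutation t-tests outside the stepwise search. So it would be wrong to say that the plan has no means of separating signal from noise. That lowers the priority but does not correct the AUC.

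Fourth, the simulations used independent normal variables, whereas clinical variables are often binary and correlated, and 17 events assumes that the drug works as designed. The exact percentages should be read in that light.

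Finally, a reader might infer that stepwise selection must give way to a penalised main-effects model. That is a choice of method. Banning interactions would also exclude a marker-by-treatment term, although sections 1.5 and 3.3 raise the question of who benefits from nintedanib.

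**Conclusion.** The concern holds as a gap in validation, of minor priority. The plan specifies a data-driven search on about 17 events and does not require that search to be repeated when performance is estimated. Read from the selected model, AUC, sensitivity, specificity and predictive values would be optimistic. With no true association, 17 events and continuous miRs, the median apparent AUC of a selected model is about 0.68–0.78, rising to 0.93 with 16 candidates and free interactions, where 0.50 is the truth.

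How often noise yields a model cannot be fixed from the documents: for the continuous version it runs from 17% to 99% over the settings tried. The optimism does not depend on settling that range, since it appeared in every setting that selected a model, though it is smaller at 30 events. The event count rests on the design rates and full accrual; the simulated figures rest on the assumed candidate numbers and independent normal markers.

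**What to change.** In section 13.7:
- List the candidate characteristics.
- Limit interactions to a short prespecified list with main effects retained. A marker-by-treatment term can be on it if that question is wanted.
- State that every data-driven step (variable reduction, Youden cut-points, forward and backward selection including any interactions, and fitting) is repeated inside each bootstrap sample or cross-validation fold.
- Report optimism-corrected AUC, calibration, sensitivity, specificity and predictive values as the performance results for every marker set, including the repeats for vitamin D, cytokines and mitochondrial DNA.

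Penalised regression is an option, not a requirement; its tuning would then go inside the resampling too.

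The cost is SAP wording, a little more code and less favourable reported performance. No extra patients, visits or samples are needed. Interactions left off the list would not be searched for.
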